9.1.2. Visit 2 (Baseline/Day 0 – Surgical procedure)

1. Investigator or clinic staff will ask the subjects if they have experienced any changes in their health since the previous visit.
2. Before the surgical procedure, the assessments below will be completed:
 - a. Clinical grading by Investigator as described in section 10.1
 - b. Tolerability assessment by the subjects as described in section.
3. The surgical area will be assessed and prepped for the procedures, followed by procedure execution by Investigator.
4. After the surgical procedure, the assessments below will be completed:
 - a. Standardized photography as described in section 10.3
 - b. Clinical grading by Investigator as described in section 10.1
 - c. Tolerability assessment by the subjects as described in section 10.2
5. Investigator or clinic staff will apply the treatment product to the surgical site followed by standard bandage.
6. Subjects will be given the treatment product with instruction of application, a diary to record usage of the treatment product, and when to contact the Investigator in case of emerging AEs.
7. Subjects will be scheduled for a follow-up visit at Day 7 or 14 (± 2 days) and dismissed from the Clinic.

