10.1 Clinical Grading by Investigator

Investigator will perform clinical grading at the surgical site on each subject at baseline (pre- and post-procedure), day 7/14, and day 28. Investigator will grade the severity of wound parameters based on a visual analog scale, described in the table below (for erythema, edema, overall wound appearance, half-point scores can be used as necessary to better describe the condition):

Parameters	Score 0	Score 1	Score 2	Score 3
Erythema	None/absent	Mild	Moderate	Severe

Protocol Version 1:

This document contains confidential, proprietary information.

Edema	None/absent	Mild	Moderate	Severe
Overall wound appearance	Excellent (absent of wound)	Good (slightly visible wound)	Fair (moderately visible wound)	Poor (marked visible wound)

Parameters	Score 0	Score 1	Score 2	Score 3	Score 4
Scabbing/crusting	None	Slight (up to 30%)	Moderate (31-60%)	Extensive (61-90%)	Almost complete or complete (91-100%)

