11. STATISTICAL ANALYSIS

A descriptive statistical summary will be provided for clinical grading and tolerability assessments. The descriptive summary will be performed for each parameter, including N, mean, median, standard deviations, minimum, and maximum of values at all applicable time points.

Mean of the change from baseline (pre-procedure) will be estimated at applicable post-baseline time point. The null hypothesis, that the mean change from baseline (pre-procedure) is zero, will be tested using methods described in the Statistical Analysis Plan table.

The following will be calculated and reported for each evaluation parameter at applicable post-baseline (pre-procedure) time point:

$$\text{Percent mean change from baseline} = \frac{(\text{postprocedure or visit mean score} - \text{baseline preprocedure mean score})}{\text{baseline preprocedure mean score}} \times 100$$

$$\text{Percent of subjects improved/worsened} = \frac{(\text{number of subjects improved/worsened from baseline preprocedure})}{\text{total number of subjects}} \times 100$$

Questionnaires will be tabulated, and the percentage of all response options (favorable and unfavorable) will be reported for each question and each timepoint.

Statistical Analysis Plan

Evaluation	Change from Baseline Pre-Procedure	Notes/Interpretation
Clinical grading	Paired t-test; If normality fails, a Wilcoxon signed-rank test will be used.	A decrease in scores indicates an improvement
Tolerability assessment	Paired t-test; If normality fails, a Wilcoxon signed-rank test will be used.	A decrease in scores or lack of significant increase indicates tolerability/safety of the treatment product
Self-assessment questionnaire	N/A	Percentage of favorable and unfavorable responses will be provided for each question.

All statistical tests will be 2-sided at significance level alpha = 0.05 unless specified otherwise. *P* values will be reported to 3 decimal places.

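### Percent mean change divides by a pre-procedure mean that can be 0 or close to 0, most clearly for overall wound appearance, and the plan has no rule for that case

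*Combined protocol and SAP*

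**What the plan says.** Section 11 introduces two percentages with "The following will be calculated and reported for each evaluation parameter at applicable post-baseline (pre-procedure) time point". The first is the percent mean change: the "postprocedure or visit mean score" minus the pre-procedure mean, divided by the "baseline preprocedure mean score", times 100. The second is the percentage of subjects improved or worsened from the pre-procedure score. The word *applicable* limits the time points, not the parameters.

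Section 11 also plans an absolute measure: "Mean of the change from baseline (pre-procedure) will be estimated at applicable post-baseline time point". For clinical grading, the analysis table adds the reading "A decrease in scores indicates an improvement".

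Section 9.1.2 fixes the order of events on Day 0. Grading and tolerability are scored first ("Before the surgical procedure, the assessments below will be completed"), then the procedure takes place, then both are scored again ("After the surgical procedure, the assessments below will be completed").

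Sections 10.1 and 10.2 define the seven parameters: erythema, edema, overall wound appearance and scabbing/crusting (investigator), and burning, itching and pain (subject). Each has 0 as its best score, meaning absent. For overall wound appearance the score 0 anchor begins "Excellent (absent of wound". Half points are allowed for all except scabbing/crusting.

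Neither Section 11 nor any other section says what to do when the denominator is 0 or small.

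**The concern.** A percentage of a group mean is informative only if that mean is well above 0. Here the denominator is measured before the event that creates the wound. If nearly all subjects score 0 then, the formula either cannot be computed or returns a figure set by one or two subjects' pre-procedure scores. An exact 0 is obvious to the analyst. A small non-zero mean is the worse case, because software prints a valid-looking percentage and Section 11 requires it to be reported. Without a rule fixed in advance, leaving it out becomes a choice made after seeing the data.

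A second consequence has the same source. A subject who scores 0 before surgery cannot go lower, so cannot count as improved from that baseline, however well the wound heals.

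**Working it through.** The plan states no expected baseline, visit mean or percent change, so there is no figure to reproduce. The formula can only be evaluated over assumed values.

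**Inputs from the documents.** N = 20 completers, 10 head/neck and 10 body (Section 6.1). Smallest step 0.5, or 1 for scabbing/crusting (Sections 10.1 and 10.2). Worst score for overall wound appearance 3 (Section 10.1).

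**Assumed.** All 20 subjects pooled, because Section 11 does not say whether the two groups are combined. Baseline means *b* from 0 to 0.50. Visit mean *v* = 0.5 unless stated.

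**Formulas.**
- Percent mean change = 100 × (v − b) / b.
- Half a point more at baseline in one subject raises *b* by 0.5/20 = 0.025. With *v* held fixed, the result moves by 100 × v × (1/b − 1/(b + 0.025)).
- Most subjects who can be above 0 at baseline = 20b/0.5 = 40b. This caps the number who can improve.

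| Baseline mean b | Percent mean change at v = 0.5 | Shift from half a point in one subject (percentage points) | Most subjects who can improve |
|---|---|---|---|
| 0 | not defined | – | 0 of 20 (0%) |
| 0.025 | +1900% | 1000 | 1 of 20 (5%) |
| 0.05 | +900% | 333 | 2 of 20 (10%) |
| 0.25 | +100% | 18 | 10 of 20 (50%) |
| 0.50 | 0% | 5 | 20 of 20 (100%) |

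For example, at b = 0.025: 100 × (0.5 − 0.025)/0.025 = 1900. At b = 0.05: 100 × (0.5 − 0.05)/0.05 = 900. The difference is 1000 points. The absolute mean change moves by only 0.025 points for the same half point, whatever the baseline.

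**Other visit means.** The shift is proportional to *v*. From b = 0.025 to 0.05 it is 200 points at v = 0.1 and 2000 at v = 1.0. At the post-procedure time point, if every wound scored 3, the formula gives 100 × (3 − 0.025)/0.025 = +11900%, or +5900% at b = 0.05.

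**Group of 10.** On a half-point scale the smallest non-zero mean is 0.5/10 = 0.05, so +900% at v = 0.5 is the most extreme computable value there.

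**How special these cases are.** With half-point scores, b = 0.025 needs 19 of 20 subjects at 0, and b = 0.05 needs at least 18. The instability is confined to baselines very close to the floor.

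**The case against.** The strongest objection is that a near-zero baseline is inferred. Section 6.3 enrols subjects whose diagnosis requires an invasive procedure, and Section 6.4 does not exclude an open or previously biopsied lesion. If 5 of 20 subjects scored 1, the mean would be 5/20 = 0.25, and half a point would move the result by only 18 points at a visit mean of 0.5. This stands. It limits the confidence, and it means that the four- and five-digit percentages are the edge of an assumed range, not a forecast. A reader might infer that the denominator is certain to be 0. The documents do not show that.

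It can also be said that the percentage is only descriptive, that N, mean, SD, minimum and maximum are reported beside it, and that any analyst would print *not calculable* for a zero. This stands for weight: no test depends on the figure. It does not deal with a small non-zero mean, where a number appears and must be reported.

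Finally, singling out overall wound appearance could be called arbitrary, since a lesion could raise that score too and the other six parameters share the 0 anchor. This is right as far as the rule goes: the gap is general. Overall wound appearance is still the clearest case, because its anchor refers to a wound that surgery has yet to make.

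**Conclusion.** The point holds as a minor one, with moderate confidence. Section 11, followed exactly, can yield an undefined or highly unstable percent mean change for any of the seven parameters. For overall wound appearance this is the expected outcome. The size rests on assumed baseline and visit means and on pooling all 20 subjects: 1000 percentage points for half a point in one subject at the extreme, fading to about 18 at a baseline mean of 0.25 and about 5 at 0.50 (visit mean 0.5).

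Two stronger readings should be avoided. One is that the inferential analysis is invalid for this reason. The mean change and the paired t-test or Wilcoxon test do not divide by the baseline mean. The other is that everything except this one percentage is untouched. If pre-procedure scores lie at the floor, the percentage improved is near 0% by construction, and the interpretation that a decrease means improvement can hardly be met. Those outputs share the baseline problem, though not the division.

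**What to change.** In Section 11:

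1. Apply one rule to all seven parameters: the percent mean change is not calculated when the denominator mean is 0 or below a minimum fixed before analysis. The absolute mean change in points, already planned, is reported instead. With a baseline at the floor, that change shows how far the site remains from its pre-procedure score, and it should be described so.
2. For overall wound appearance, calculate the Day 7/14 and Day 28 percent change, and the percentage improved or worsened, from the Day 0 post-procedure score. Label them as recovery since surgery. Apply the same minimum, because post-procedure means are not documented either. Do not calculate the percent change at the post-procedure time point, where it is 0% by construction.

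The cost is small but not nil. No new data are needed. Some percentages will go unreported. Recovery since surgery is not the same as return to the pre-procedure state. The minimum is a choice that limits instability without removing it. Taking 0.5 as an example, half a point in one of 20 subjects still moves the result by 300 × (1/0.50 − 1/0.525) = about 29 points at a visit mean of 3.0. A whole scabbing/crusting point moves it by 300 × (1/0.50 − 1/0.55) = about 55. Because the analysis plan is part of the protocol, and this change is neither logistical nor administrative, Section 14.4 calls for an amendment with IRB approval.

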6. SELECTION AND DISPOSITION OF STUDY POPULATION

6.1 Number of Subjects

A maximum 20 subjects to complete the study, in which 10 subjects with dermatologic procedure on the head/neck and 10 subjects with dermatologic procedure on the body.

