9. STUDY PROCEDURES

The table below represents a summary of the study procedures and evaluation schedule:

1. Visit 1 – Screening
2. Visit 2 – Baseline/Day 0 (surgical procedure)
3. Visit 3 – Day 7 (for head/neck group) or Day 14 (for body group)
4. Visit 4 – Day 28

Test design / flow chart	Visit 1	Visit 2		Visit 3	Visit 4
	Screening	Baseline Day 0 Pre-procedure	Baseline Day 0 Post-procedure	Day 7 or Day 14	Day 28
ICF and qualification/enrollment	X				
Photo consent	X				
Demographics/Med History	X				
Concomitant Meds.	X				
Inclusion and exclusion criteria	X				
CRF		X	X	X	X
Investigator grading		X	X	X	X
Subjective tolerability grading		X	X	X	X
Standardized photography		X	X	X	X
Self-assessment questionnaire				X	X
AE reporting			X	X	X
Treatment product		W	D	W	C/W
Daily diaries			D	C/D	C

For treatment product and/or daily diaries: W = Weigh, D = Distribute, C = Collect

Protocol Version 1:

This document contains confidential, proprietary information.

Protocol GLI.04.US.SL.017

CONFIDENTIAL

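### Section 11's change tests ignore the fixed 10:10 head/neck–body quota; a location term at Day 28 and Day 0 post-procedure would be a cheap precision gain

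*Combined protocol and SAP*

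**What the plan says.** Section 6.1 caps the study, "A maximum 20 subjects to complete the study", and splits that number by site of procedure, "in which 10 subjects with dermatologic procedure on the head/neck and 10 subjects with dermatologic procedure on the body". Section 9 treats the two as named groups with different interim visits, "Day 7 (for head/neck group) or Day 14 (for body group"), and then a common Day 28 visit.

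Section 11 states one null for each graded parameter: "The null hypothesis, that the mean change from baseline (pre-procedure) is zero, will be tested". The method for both clinical grading and tolerability is "Paired t-test; If normality fails, a Wilcoxon signed-rank test will be used", and "All statistical tests will be 2-sided at significance level alpha = 0.05 unless specified otherwise". It provides no location term, no test by location and no summary by location. The percentage improved or worsened is taken over the "total number of subjects". For burning, itching and pain, the analysis table counts the absence of a significant rise as evidence of tolerability. The plan states no power target, effect size, SD of change or expected difference between locations.

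**The concern.** Because location is filled by quota, it is a design stratum and not a random feature of the sample. With the split fixed at 10:10, a difference between the two location means does not add to the sampling error of the overall mean change. It does add to the SD of the 20 pooled changes, which is what the paired t-test uses, so the error bar is too wide whenever the locations change by different amounts. The signed-rank fallback loses power in the same way. The normality check is also affected, because it is applied to a mixture of two groups that may be centred differently.

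What is at stake is power in a study with at most 20 completers. It matters most for the tolerability items: where a non-significant rise is read favourably, a test with less power makes the favourable reading easier to reach. The design also recruits equally from two locations without planning an estimate for either at Day 28, the only follow-up visit on a common day.

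**Working it through.** **Inputs from the documents.** 20 completers, 10 per location (Section 6.1); a one-sample test of change, two-sided alpha 0.05, no location term (Section 11). There is no power figure to reproduce.

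**Inputs assumed.** Within-location SD of change s_w = 1, equal in both locations; near-normal changes; 10:10 achieved; d, the location difference in mean change in units of s_w, varied from 0 to 2; overall mean change 0.6, 0.8 or 1.0 s_w.

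**Step 1: standard error.** With the split fixed, the true variance of the overall mean is s_w²/20. The two location means lie d·s_w/2 either side of the overall mean, so the expected pooled sample variance is

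s_w² + 20·(d·s_w/2)²/19 = s_w²·(1 + 5d²/19).

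The paired-t standard error is therefore too large by sqrt(1 + 5d²/19). At d = 1 this is sqrt(24/19) = 1.124. At d = 0.25, 0.5, 0.75 and 1.5 it is 1.008, 1.032, 1.071 and 1.262.

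**Step 2: cost of stratifying.** The stratified test uses the pooled within-location SD on 18 df, critical t 2.101 against 2.093 on 19 df. Its interval is the shorter one once d exceeds about 0.17. At d = 0 it gives up about 0.3 points of power.

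**Step 3: power, plan's paired t-test versus stratified test** (simulation, fixed 10:10, agreement to within simulation error across repeat runs):

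| Mean change | d = 0.25 | d = 0.5 | d = 0.75 | d = 1 |
|---|---|---|---|---|
| 0.6 SD | 71.5% vs 71.7% | 70% vs 72% | 67% vs 72% | 63% vs 72% |
| 0.8 SD | – | 91.5% vs 92.3% | – | 87.9% vs 92.0% |
| 1.0 SD | – | 98.7% vs 98.8% | – | 97.8% vs 98.8% |

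At d = 1.5 and 0.6 SD it is 53% vs 72%. At 0.6 SD and d = 1, the chance of missing a true change goes from about 28% (stratified) to 37% (plan).

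**Step 4: half-point scores.** With changes rounded to half points, SD 0.75 before rounding and mean change 0.5 grade, the figures are 76.4% vs 79.1%, 72.2% vs 79.2% and 66.1% vs 79.0% for location differences of 0.5, 0.75 and 1.0 grade.

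**Step 5: signed-rank fallback.** At a mean change of 0.662 SD (80% power for the stratified t-test), the signed-rank test has 78%, 76%, 70% and 44% power at d = 0, 0.5, 1 and 2.

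**Step 6: a rank-free replacement for the fallback.** Flipping the signs of within-location residuals and comparing the raw intercept has a true size of about 8% with normal changes. Recomputing the within-location SD at each flip, so that the studentised intercept is compared, brings it to about 5%. With strongly skewed (exponential) changes the studentised version has size of about 8%, and so does the t-test.

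**The case against.** The strongest reply is that an unstratified paired t-test is conventional and valid in a small single-arm study, and that the plan breaks no promise because it states no power. That stands. Three stronger readings are tempting, and the documents do not support them.

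*The test does not have its stated 5% error rate.* A reader might infer this because the simulated size falls to about 4.4% at d = 0.5 and 2.9% at d = 1. Those figures need an overall mean of exactly zero with d above zero, so that one location improves by as much as the other worsens. If neither location changes, the size is 5%. Where it departs from 5% under the assumed near-normal changes, it is on the conservative side.

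*The plan itself shows that the locations differ.* The different interim days apply to Visit 3 only. They say nothing direct about change at Day 28 or at Day 0 post-procedure, and could equally be meant to catch both groups at a similar stage of healing. Pairing already removes any constant location difference in score level.

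*The loss is large in general.* It is large only with a sizeable d and a middling effect. Wound grades immediately after the procedure are compared with pre-procedure skin, so those changes may well be big enough that power is not the constraint.

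It can also be said that reading non-significance as tolerability is weak at this sample size with or without a location term. That is true: the term reduces the weakness and does not cure it. Procedure type and centre are further sources of variation, but neither has a fixed quota.

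**Conclusion.** The point holds as a cheap improvement in precision. The quota is fixed, the analysis ignores it, and the direction of the effect follows from algebra: if mean change differs by location at a shared time point, the standard error is too wide and power is lost. The size cannot be derived from the documents. Under the stated assumptions it is negligible up to about d = 0.25, small at d = 0.5, and worth having from about d = 0.75 when the overall change is near 0.6 SD. By 1.0 SD it is about 1 point even at d = 1. It is not a validity error. The best reason to act is the tolerability rule, under which lower power favours the product, together with the lack of any planned Day 28 estimate by location. The figures rest on 10:10 completion, equal within-location variances and near-normal changes, whereas the actual scores are short ordinal scales, most of them with half points.

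**What to change.** In Section 11, for Day 28 and Day 0 post-procedure:

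- Replace the unstratified paired t-test with a linear model of the change score on location coded +0.5/−0.5. Report the intercept, which is the equally weighted mean of the two location means (18 df with 20 completers), with its 95% CI and p-value.
- Report the two location means with CIs from the same model.
- Check normality on the model residuals, not on the pooled changes.
- If normality fails, use a sign-flip test on the within-location residuals based on the studentised intercept, recomputing the within-location SD at each flip. Do not use the raw intercept. State that the test is approximate and that it offers no protection beyond the t-test when changes are strongly skewed.

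The cost is SAP wording, since location already defines the groups. There are two downsides. One degree of freedom is spent, about 0.3 points of power if the locations do not differ. And because 20 is a maximum, completers may end up unequal; the intercept then weights the locations equally and no longer equals the plain mean change in Section 11, so the SAP should say which quantity is being estimated.

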5. STUDY OBJECTIVE AND CLINICAL HYPOTHESIS

5.1 Study Objective

To evaluate safety and efficacy of a Healing Ointment in skin improvement after dermatologic procedures such as Mohs surgery, skin biopsy, excision on the head/neck or body.

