10.2 Tolerability Assessments

Tolerability assessments will be performed by subjects at the surgical site at baseline (pre- and post-procedure), day 7/14, and day 28. Subjects will grade the degree of irritation parameters that they experience based on a 4-point analog scale, described in the table below (with half-point scores used as necessary to better describe the clinical condition):

Parameters	Score 0	Score 1	Score 2	Score 3
Burning	None	Mild	Moderate	Severe
Itching	None	Mild	Moderate	Severe
Pain	None	Mild	Moderate	Severe

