12. ADVERSE EVENTS

Throughout the course of the study, all adverse events will be monitored and reported on an adverse event CRF/eCRF without omitting any requested and known information. When AEs occur, the main concern is the safety of the study subjects. At time of the informed consent signature, each subject must be given the name and phone number of investigational site personnel for reporting AEs and medical emergencies.

At each visit, after the subject has had the opportunity to spontaneously mention any problems, the investigator should inquire about AEs by asking the standard questions:

Protocol Version 1:

This document contains confidential, proprietary information.

Protocol GLI.04.US.SL.017

CONFIDENTIAL

- “Have you had any health problems since your last study visit?”
- “Have there been any changes in the medicines you take since your last study visit?”

AEs should be reported for any clinically relevant change, as determined by the Investigator, in concomitant medication(s) that is the result of an untoward (unfavorable and unintended) change from baseline in a subject's medical health following exposure to the study treatment.

Changes from baseline in any protocol-specific parameter evaluated during the study are to be reviewed by the Investigator. In addition, the subject's responses to any questionnaire utilized during the study are to be reviewed by the investigator. Any untoward (unfavorable and unintended) change from baseline in a protocol-specific parameter or question response that is clinically relevant, in the opinion of the investigator, is to be reported as an AE. These clinically relevant changes will be reported regardless of causality.

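### The SAP treats a fall, or a non-significant rise, in burning, itching or pain as showing tolerability/safety; with at most 20 completers, one arm and no margin, neither result shows it

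*Combined protocol and SAP*

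**What the plan says.** Section 5.1 makes safety part of the objective: "To evaluate safety and efficacy of a Healing Ointment in skin improvement after dermatologic procedures". Section 10.2 has subjects score burning, itching and pain from 0 (none) to 3 (severe), "with half-point scores used as necessary to better describe the clinical condition". Section 6.1 sets the size: "A maximum 20 subjects to complete the study", split as 10 head/neck and 10 body. There is one product and no comparator.

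Section 11 gives the test: "The null hypothesis, that the mean change from baseline (pre-procedure) is zero, will be tested". The method is a paired t-test, or a Wilcoxon signed-rank test if normality fails, two-sided at alpha 0.05. The interpretation entry for tolerability reads: "A decrease in scores or lack of significant increase indicates tolerability/safety of the treatment product".

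Section 11 also plans the minimum and maximum for each parameter and a percentage based on the "number of subjects improved/worsened from baseline preprocedure". Section 12 asks the investigator to review score changes, and an unfavourable change "that is clinically relevant, in the opinion of the investigator, is to be reported as an AE". Sections 12.1.2, 12.4 and 12.4.1 cover undesirable effects, and the Day 7/14 questionnaire in Appendix II asks about irritation. The interpretation sentence refers to none of these.

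**The concern.** The sentence has two limbs, and neither supports the conclusion drawn.

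- **Non-significance limb.** A difference test that does not reject has not shown that the increase is small. Without a margin or an interval criterion, fewer subjects and noisier scores make the favourable reading easier to reach.
- **Decrease limb.** A lower mean carries no condition on individuals, so it can coexist with subjects who became severe. It also requires no minimum size and no significance.

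The reference is the pre-procedure score, so symptoms from the surgery itself enter the change. With one arm, neither a rise nor its absence isolates the product.

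The Day 0 post-procedure scores cannot reflect the product at all. In Section 9.1.2 they are taken at step 4, and only at step 5 is it the case that "Investigator or clinic staff will apply the treatment product to the surgical site followed by standard bandage". The change formula in Section 11 nevertheless includes post-procedure scores, and the interpretation sentence excludes no time point.

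At stake is a statement on one of the two stated objectives that the data may not support.

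**Working it through.** **Inputs from the documents.** At most 20 completers (Section 6.1); scale 0 to 3 with half points (Section 10.2); zero-change null, two-sided alpha 0.05, paired t or Wilcoxon (Section 11). The documents give no margin, power, SD or expected symptom distribution, so there is no planned figure to reproduce. The effect sizes and score patterns below are assumptions.

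**1. What the test can miss.** Power of the paired t-test with n = 20 is 1 - F(t(0.975, 19); df 19, noncentrality d x sqrt(20)), where d is the true mean increase in SD units of the change.

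| d (assumed) | 0.2 | 0.3 | 0.5 | 0.8 |
|---|---|---|---|---|
| Power | 13% | 25% | 56% | 92% |

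A true increase of 0.5 SD would be non-significant, and so read as tolerable, about 44% of the time (100% - 56%).

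**2. Score patterns, n = 20, one symptom, one visit.** The paired t is mean/(SD/sqrt(20)) with 19 df. The Wilcoxon test drops zeros and uses the tie-corrected variance (sum of squared ranks)/4. The SAP does not say which version applies, so p is given without continuity correction / with a 0.5 correction / exact by sign-flip enumeration.

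Pattern A in full (3 subjects go 0 to 3, 17 unchanged):
- Mean = 9/20 = 0.45. Variance = (27 - 20 x 0.45^2)/19 = 22.95/19 = 1.208, so SD = 1.099.
- SE = 1.099/sqrt(20) = 0.246; t = 0.45/0.246 = 1.83; p = 0.083.
- 95% CI = 0.45 +/- 2.093 x 0.246 = -0.06 to 0.96.
- Wilcoxon: three tied ranks of 2, so W = 6, expected 3, variance 12/4 = 3. Then z = 3/1.732 gives p = 0.083, z = 2.5/1.732 gives p = 0.149, and exact p = 2/2^3 = 0.25.

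| Pattern | Mean change (SD) | t p | Wilcoxon p | Sentence satisfied? |
|---|---|---|---|---|
| A: 3 worse by 3, 17 unchanged | +0.45 (1.099) | 0.083 | 0.083 / 0.149 / 0.25 | Yes, with 15% severe |
| B: 3 worse by 0.5, 17 unchanged | +0.075 (0.183) | 0.083 | 0.083 / 0.149 / 0.25 | Yes |
| C: 6 worse by 0.5, 14 unchanged | +0.15 (0.235) | 0.010 | 0.014 / 0.020 / 0.031 | No, if none reaches 3 |
| D: 3 go 0 to 3, 10 improve by 1, 7 unchanged | -0.05 (1.395) | 0.87 | 0.48 / 0.51 / 0.53 | Yes, on both limbs, with 15% severe |

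A and B give identical p-values because both tests are unaffected by scale: the size of the worsening does not enter. C fails the criterion with one third of A's mean increase (0.15/0.45; 95% CI for C 0.04 to 0.26). In C nobody becomes severe when the half-point rises start from low scores. The criterion can therefore rank outcomes in the wrong order.

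**3. How far A can be pushed.** Add three subjects worse by 0.5 (mean 0.525): t p = 0.043, Wilcoxon 0.024 / 0.032 / 0.031, significant throughout. Add instead two subjects worse by 1 (mean 0.55): t p = 0.037, Wilcoxon 0.038 / 0.053 / 0.0625, a mixed result.

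**4. Precision of proportions (Clopper-Pearson).** 3/20 = 15%, 95% CI 3.2% to 37.9%. For 0/20 the upper limit is 1 - 0.025^(1/20) = 16.8%.

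**The case against.** The best defence is that safety does not rest on this sentence. A score of 3 would appear as a maximum, percent worsened is planned, and clinically relevant worsening is to be reported as an adverse event regardless of causality. The wording sits in a notes column of a small single-arm study and is not called a success criterion. This stands as a limit on the harm: the cases would be visible. It does not rescue the sentence, which draws a tolerability/safety conclusion and makes none of those outputs a condition for it.

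The patterns are also chosen. A needs the other 17 subjects to show little or no change, and step 3 shows how easily that breaks. D needs at least 10 subjects scoring 1 or more on that symptom before surgery, which nothing in the documents suggests. Surgical symptoms would tend to raise scores and so work against a favourable reading. These points limit how often the sentence would mislead. They do not touch the logical fault, which depends on no pattern.

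The changes in A, C and D are clearly non-normal, so Wilcoxon would probably apply, although the SAP names no normality test. A and D remain non-significant under every Wilcoxon version. The related point, that a t interval on mostly zero changes is only approximate, is fair and is taken up in the fix.

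Finally, deleting only the non-significance limb would be a smaller edit. Pattern D shows why that is not enough.

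**Conclusion.** The concern holds and should be fixed. As written, Section 11 turns non-rejection, or any fall in a mean, into a conclusion on a stated objective, with at most 20 completers, one arm and no margin. In the illustrative case, 3 of 20 subjects becoming severe (15%, exact 95% CI 3.2% to 37.9%) meets the criterion under the t-test and every Wilcoxon version, provided the others change little. The size of the problem in practice is uncertain because the documents give no expected symptom distribution or SD. The consequence is a misleading statement and not concealed data.

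**What to change.** Replace the whole tolerability interpretation sentence, so that neither a lower mean nor a non-significant increase is by itself a tolerability/safety verdict. For each of the three symptoms at Visit 3 and Day 28, report:

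- the mean change from pre-procedure with its 95% CI, naming in the SAP how the interval is built when the changes are non-normal;
- the already planned percent worsened, with an exact 95% CI;
- a shift table from pre-procedure score to visit score, half points as recorded, so that worsening to moderate or severe is visible.

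State that these are interpreted together with the adverse event and undesirable-effect data, and that a single arm cannot separate product symptoms from surgical ones. State that the Day 0 post-procedure scores precede the first application and do not support product tolerability conclusions; they can still be shown as a description of symptoms after surgery and before product. If the sponsor wants a formal verdict, it needs a margin stated and justified in advance.

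The cost is SAP wording and one table layout (3 symptoms at 2 visits) from data already collected, with no added visits or subjects. The resulting statement will be more guarded: even 0 of 20 worsened leaves an upper 95% limit of 16.8%.
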